7.2.2 Chemoradiation will be administered over 5 weeks

7.2.2.1 The intent is to deliver 45 Gy in 1.8 Gy/fraction, 5 days a week for 5 weeks, to the entire gastric bed (including anastomosis) and draining lymph nodes.

7.2.2.2 Chemotherapy with radiation will consist of a single agent fluoropyrimidine, either capecitabine (per section 7.2.2.2.1) or 5-fluorouracil (per section 7.2.2.2.2), at the treating physician's discretion.

7.2.2.2.1 Capecitabine will consist of 750 mg/m², PO BID on days of radiation

AGENT	DOSE	ROUTE	DAYS	INTERVAL
Capecitabine	750 mg/m ²	PO (BID)	Days of Radiation	5-weeks

7.2.2.2.2 5-fluorouracil will be dosed as 200 mg/m²/day, IV continuous infusion on days of radiation

AGENT	DOSE	ROUTE	DAYS	INTERVAL
5-fluorouracil	200 mg/m ²	IV (over 1 day)	Days of radiation	5-weeks

7.2.2.3 Criteria for proceeding with treatment and managing side effects will be as in 5.1.3.

7.3 Chemotherapy after chemoradiation: After finishing chemoradiation (section 7.2.2), subjects will receive two cycles of chemotherapy alone, as in 7.2.1. Changing to the alternative fluoropyrimidine (capecitabine or 5-fluorouracil) from what was used previously is permissible at the discretion of the treating investigator.

7.4 Chemotherapy side effect management

7.4.1 All patients will receive anti-emetic prophylaxis, IV, on day 1 of IV chemotherapy.

7.4.2 All patients will be prescribed oral anti-emetics as needed (per investigator discretion and standard clinical care).

7.4.3 Patients that develop diarrhea can be managed using as needed loperamide or other anti-diarrheals, at the discretion of the treating physician.

7.4.4 On Day 1 of each cycle (or, up to 2 days before Day 1), patients must meet the following criteria in order to proceed with treatment:

7.4.4.1 ANC ≥ 1,500/mm³

7.4.4.2 Platelets \geq 75,000/mm³

7.4.4.3 Hemoglobin \geq 8.0 gm/dL

7.4.4.4 Resolution of any non-hematologic toxicity to adequately controlled to the satisfaction of the treating investigator.

7.4.5 If a patient does not meet criteria in Section 7.4.4 on day 1 of a cycle, treatment should be held until resolution of such symptoms or signs to meet the criteria in Section 7.4.4.

7.4.6 Additional supportive care will be given based on the clinical judgment of the treating investigator, per standard clinical practice.

7.4.7 Chemotherapy dose modifications (reductions or delays) due to toxicity should be as per standard clinical practice, at the discretion of the treating investigator.

8.0 CRITERIA FOR STUDY CONTINUATION OR DISCONTINUATION

All patients who are enrolled on the study and begin any of their intended post-operative adjuvant therapy will be counted as evaluable for the study. This inclusion will be regardless of how much of the postoperative treatment they ultimately receive.

Criteria for discontinuation of post-operative treatment will be:

- a) Unacceptable toxicity
- b) Treatment delay due to toxicity > 2 weeks.
- c) Treatment delay for any other reason > 3 weeks.

Patients who discontinue treatment for these reasons will remain on protocol and will move on to surveillance/follow-up for disease recurrence

Disease recurrence, will be defined as radiographic tumor evidence detected by surveillance imaging. Confirmation of recurrence by biopsy will be at the discretion of the treating physician.

If a subject has disease recurrence during surveillance / follow-up, then further study follow-up can be discontinued; the subject will come off-study, and can be followed per standard clinical care at the investigator's discretion.

The patient may withdraw from the study at any time for any reason. Similarly, an investigator may remove a patient from the study for non-compliance with study protocol at any time. Patients removed from the study for these reasons will be replaced.

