5.0 SUBJECT ELIGIBILITY: Patient Initials (L,FM): _____

5.1 Inclusion Criteria:

- 1) Must have pathologically-proven adenocarcinoma of the stomach or gastroesophageal (GE)-junction, stage M0, as established by both imaging and surgical pathologic staging.

Imaging: Clinical stage of M0 will be established by either CT (chest with contrast and abdomen/pelvis with and without contrast), or CT/PET (skull base to mid-thigh). This is standard post-surgery imaging.

Surgery: Surgical pathologic staging must be M0.

- 2) Must have completed 3 cycles of neo-adjuvant chemotherapy. Either CAPEOX or

FOLFOX is allowed. Dose modifications are allowed, but all 3 cycles must have been completed.

- 3) Must have undergone a surgical resection with definitive intent, either by open or laparoscopic resection of the primary gastric or GE junction cancer. Patients must have undergone a total gastrectomy, subtotal gastrectomy, or distal gastrectomy (depending on the location of primary gastric lesion) with at least a modified D2 lymphadenectomy.
- 4) Must be deemed as a good candidate for adjuvant chemotherapy or chemoradiation (to start within 3 months of surgery), in the opinion of the treating investigator. Plan must be to start adjuvant therapy within 90 days of surgery; adjuvant treatment cannot begin more than 90 days after surgery.
- 5) Must have diagnostic biopsy tissue (pre-neoadjuvant chemo) available for genetic testing.
- 6) Must have surgical tissue (post-neoadjuvant chemo) available for genetic testing.
- 7) Must be ≥ 18 years of age.
- 8) Must be able to provide informed consent.
- 9) Must have adequate kidney, liver, and bone marrow function, within 28 days prior to registration, as follows:
 - i. Hemoglobin ≥ 8.0 gm/dL
 - ii. Absolute neutrophil count (ANC) ≥ 1500 cells/mm³
 - iii. Platelet count $\geq 75,000$ /mm³
 - iv. Calculated creatinine clearance of > 60 mL/min/m², calculated as follows:
For males = $\frac{(140 - \text{age [years]}) \times (\text{body weight [kg]})}{(72) \times (\text{serum creatinine [mg/dL]})}$
For females = $0.85 \times$ male value
 - v. Total bilirubin ≤ 1.5 times upper limit of normal (ULN)
 - vi. AST (SGOT) and ALT (SGPT) ≤ 3.0 times the ULN
- 10) Must have life expectancy of greater than 3 months.
- 11) Must have an ECOG performance status 0-2.

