7.0 TREATMENT PLAN

Preoperative chemotherapy: Patients will have received 3 cycles of neo-adjuvant chemotherapy (either CAPEOX or FOLFOX) at the treating physician's discretion. Dose modifications are allowed per standard clinic practice.

After the completion of the preoperative therapy, patients without evidence of obvious metastatic disease will undergo a surgical resection with definitive intent, either by open or laparoscopic resection of the primary gastric or GE junction cancer.

After completion of surgery, patients will be reviewed for eligibility. Eligible subjects will be registered to the study and assigned to Arm 1 or Arm 2.

Treatment should start within 3 months of surgery.

All adjuvant treatment regimens (both Arm 1 and Arm 2) are to be administered per standard clinic practices, including infusion duration times, dose modifications, treatment delays, and supportive care.

7.1 Arm 1: Postoperative chemotherapy, for those patients with node negative disease at time of surgery, will consist of three additional cycles of chemotherapy. Subjects can receive either CAPEOX or FOLFOX (regardless of the neo-adjuvant regimen), following the same dosing guidelines and management as below. Changing to the alternative fluoropyrimidine (capecitabine or 5-fluorouracil) from what was used pre-operatively is permissible at the discretion of the treating investigator.

7.1.1 CAPEOX will be dosed on a 21-day cycle:

AGENT	DOSE	ROUTE	DAYS	INTERVAL
Oxaliplatin	130 mg/m ²	IV	Day 1	21-day cycle
Capecitabine	625 mg/m ²	PO (BID)	Days 1-5, 8-12, 15-19	21-day cycle

or

[figure not shown]
AGENT	DOSE	ROUTE	DAYS	INTERVAL
Oxaliplatin	130 mg/m ²	IV	Day 1	21-day cycle
Capecitabine	1000 mg/m ²	PO (BID)	Days 1-14	21-day cycle

7.1.2 FOLFOX will be dosed on a 14-day cycle. Agents are to be given in this order, according to standard clinic practice.

AGENT	DOSE	ROUTE	DAYS	INTERVAL
Oxaliplatin	85 mg/m ²	IV	Day 1	14-day cycle
Leucovorin	400 mg/m ²	IV	Day 1	14-day cycle
5-fluorouracil*	400 mg/m ²	IV bolus	Day 1	14-day cycle
5-fluorouracil*	2400 mg/m ²	Continuous IV infusion	Day 1-3	14-day cycle

* 5-fluorouracil will be dosed as 400 mg/m² through IV bolus, followed by 2400 mg/m² through continuous IV infusion, starting Day 1

7.2 Arm 2: Postoperative chemoradiation, for those patients with node positive disease at time of surgery, will consist of one cycle of chemotherapy, followed by concurrent chemoradiation (5 weeks), and followed by two additional cycles of chemotherapy.

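### The evaluable set admits only patients who begin therapy, so registered patients who never start drop out of the primary feasibility rate and can only raise it or leave it unchanged

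*Combined protocol and SAP*

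**What the plan says.** - **Order of events.** Section 7.0 reviews eligibility after surgery and then says: "Eligible subjects will be registered to the study and assigned to Arm 1 or Arm 2". The first adjuvant dose comes later.
- **Analysis set.** Section 8.0 gives the only definition: patients who are "enrolled on the study and begin any of their intended post-operative adjuvant therapy will be counted as evaluable for the study". It adds: "This inclusion will be regardless of how much of the postoperative treatment they ultimately receive".
- **Stops and replacement.** Section 8.0 says of stops for toxicity or delay: "Patients who discontinue treatment for these reasons will remain on protocol". Of voluntary withdrawal and removal for non-compliance it says: "Patients removed from the study for these reasons will be replaced".
- **Primary endpoint.** Section 10.0 defines it as the proportion of patients completing the therapy indicated by nodal status, without mentioning the evaluable set. It plans on 30 patients receiving chemoradiation and 10 receiving chemotherapy. All enrolled patients are named only for descriptive summaries.
- **Criteria.** Section 10.0 calls the treatment feasible if at most 30% cannot complete it. It also asks that at most 30% of node-negative patients be unable to receive chemotherapy, and that a majority of node-positive patients receive chemoradiation in full.
- **Objective.** Sections 2.1 and 10.0 state it as the feasibility of both enrolling and receiving the assigned therapy.

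**The concern.** A registered patient who never starts cannot be a completer. If such patients are left out, only failures leave the denominator, and the rate can move only towards feasible.

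The protocol has routes to this outcome. Blood counts are checked again by Day 1, when "patients must meet the following criteria in order to proceed with treatment" (Section 7.4.4); if they do not, "treatment should be held until resolution of such symptoms or signs to meet the criteria in Section 7.4.4" (Section 7.4.5). Section 5.1 also says that "adjuvant treatment cannot begin more than 90 days after surgery", and Section 8.0 lets patients withdraw at any time.

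A rate among starters describes how well therapy is tolerated once begun. It does not fully answer the stated objective or the node-negative criterion, both of which concern receiving therapy. The rate matters because Section 2.3 uses it to justify a larger trial.

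Replacement is a second, smaller gap. Section 8.0 keeps every starter evaluable, yet replaces some patients without saying how the two rules combine.

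**Working it through.** **1. The plan's own figure.** The 95% Wilson half-width at p = 0.5 is z·sqrt(p(1−p)/n + z²/(4n²)) / (1 + z²/n), with z = 1.96. For n = 30 it is 16.8% and for n = 10 it is 26.3%. These agree with the 17% and 26.5% upper limits in Section 10.0. The precision was thus worked out on 30 and 10 patients, described as those receiving treatment, which fits a starters-only set.

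**2. Direction.** Let N be registered patients, k never-starters and C completers. The starters-only rate is C/(N−k) and the registered rate is C/N. Because C counts no never-starter, C/(N−k) ≥ C/N, with equality only if k = 0 or C = 0.

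**3. Verdict at the threshold.** If accrual continues until the planned number have started, k omitted failures change the result as follows.

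| Starters-only result | Criterion | Never-starters counted |
|---|---|---|
| 21/30 = 70.0% | 70% | 1 reverses: 21/31 = 67.7% |
| 22/30 = 73.3% | 70% | 2 reverse: 22/32 = 68.8% |
| 23/30 = 76.7% | 70% | 3 reverse: 23/33 = 69.7% |
| 7/10 = 70.0% | 70% | 1 reverses: 7/11 = 63.6% |
| 16/30 = 53.3% | majority | 1 does not: 16/31 = 51.6%; 2 do: 16/32 = 50.0% |

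If registration is instead fixed at 30, and 3 never start and 19 complete, the starters-only rate is 19/27 = 70.4% (met) and the registered rate is 19/30 = 63.3% (not met).

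**4. Chance of declaring feasibility.** Assumptions, none given in the documents: true completion among registered patients is π = 0.60, and a share f of non-completers never start. Never-starters are then (1−π)f of those registered, and the expected starters-only rate is p = π / (π + (1−π)(1−f)). For f = 0.10, p = 0.60/(0.60 + 0.40 × 0.90) = 0.60/0.96 = 0.625. Rows with a count use the exact binomial P(X ≥ count) at p, with never-starters replaced so that the planned number is counted.

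| | f = 0 | 5% | 10% | 20% |
|---|---|---|---|---|
| Never start, % of registered | 0 | 2 | 4 | 8 |
| Expected reported rate, % | 60.0 | 61.2 | 62.5 | 65.2 |
| Arm 2, 70% bar (21/30) | 0.18 | 0.21 | 0.26 | 0.37 |
| Arm 2, majority (16/30) | 0.82 | 0.86 | 0.89 | 0.94 |
| Arm 1, 70% bar (7/10) | 0.38 | 0.41 | 0.45 | 0.52 |
| Both arms pooled, 70% bar (28/40) | 0.13 | 0.16 | 0.21 | 0.32 |
| Arm 2, 70% bar, 30 registered, none replaced | 0.18 | 0.19 | 0.22 | 0.32 |

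In the last row the number of never-starters is binomial(30, (1−π)f), and the bar is 70% of those who remain, rounded up.

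Sensitivity to π, Arm 2 at 21/30 with replacement: for π = 0.55 the four values are 0.07, 0.09, 0.12 and 0.19; for π = 0.65 they are 0.36, 0.41, 0.46 and 0.58.

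**5. Replacement.** Suppose 3 starters withdraw before completing and are replaced, and 21 patients complete. Dropping the 3 gives 21/30 = 70.0%; keeping them gives 21/33 = 63.6%. The direction is not fixed in general: dropping someone who completed therapy and later left follow-up would lower the rate.

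**The case against.** The strongest reply is that the exclusion is inferred. Section 8.0 says who is evaluable and does not say that nobody else is; Section 10.0 never refers to that set. Its node-negative criterion, about patients unable to receive chemotherapy, could even be read as counting never-starters already. This stands as a point about the text. But no passage states another denominator for the completion rate, and that criterion, so read, would conflict with a starters-only rate. Either way the denominator has to be written down.

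Second, much is already protected. In Arm 2 a chemotherapy cycle precedes radiation, so a patient who starts and then goes without radiation remains counted as a non-completer. So do toxicity and delay stops. For a pilot concerned with tolerance, a started-therapy set is defensible. That is a good reason to keep it as a supporting figure, but it does not cover the receiving part of the objective.

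Third, never-starting may be rare. Eligibility requires a good candidate with a plan to start in time, the Day 1 count thresholds equal those met at screening, and failing them leads to a hold. This stands and favours low f. At f = 5% the expected rate moves by 1.2 points, small beside the plan's interval of about ±17 points. Replacing every never-starter is also an assumption, since Section 8.0 replaces only withdrawals and non-compliance removals.

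Finally, on its face a replaced starter stays evaluable, so the replacement point is only a request for clarity. That is accepted.

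**Conclusion.** The concern holds. On the natural reading, the primary rate omits registered patients who can only be failures, so the omission either favours feasibility or has no effect. That direction is certain for any positive number of never-starters, provided at least one patient completes. The size is not known from the documents. With 60% true completion, and 5% to 20% of non-completers never starting, the reported rate is inflated by 1.2 to 5.2 points. The chance that Arm 2 passes the 70% bar rises from 0.18 to between 0.21 and 0.37 with replacement, or between 0.19 and 0.32 without it. The lower end is the more plausible. A single omitted failure changes the verdict only when the result sits exactly on the 70% threshold. Replacement biases the rate upward only if replaced starters who did not complete are dropped, and nothing in the plan says that they are. This should be fixed, because the rate decides whether a larger trial follows and the repair is cheap.

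**What to change.** In Sections 8 and 10:

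1. Define the primary denominator as all patients registered and assigned to each arm, whichever feasibility criterion is applied.
2. Count as non-completers those who do not start within the protocol's existing window, and those who withdraw or are removed before completing assigned therapy.
3. State that replacement adds a patient and never takes one out of the denominator, and that a patient who completes therapy and later leaves surveillance remains a completer.
4. Report the start rate among registered patients and the completion rate among starters as supporting figures.

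This is a wording change, with no new procedures or data. The reported rate may be somewhat lower and the denominator may exceed 40. Patients who do not start for reasons unrelated to tolerability will count as failures; the two supporting rates show that component separately.

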2.0 SYNOPSIS

2.1 Primary Objective:

To determine the feasibility of patients enrolling and receiving either postoperative chemoradiation or chemotherapy alone, based upon nodal status at surgery, following preoperative chemotherapy.

2.2 Secondary Objectives:

To evaluate the rate of cancer recurrence in patients assigned to treatment based upon node status

To explore the potential correlation between changes in expression of a pre-specified panel of genes identified as relevant to gastrointestinal cancers in response to preoperative chemotherapy, using presence of nodal involvement at time of surgery as an indicator of response.

2.3 Primary Endpoint:

The proportion of patients who would meet the criteria would be estimated to demonstrated successful enrollment and treatment of therapies including postoperative chemotherapy or chemoradiation as indicated by the nodal features, which would justify development of a study powered to demonstrate survival benefit to patients using this approach. Expect that no more than 30% of patients will be unable to complete all protocol therapy.

2.4 Secondary Endpoints:

The recurrence rate while on trial will be reported for the two arms of the trial, and compared to historical controls

Observation of changes in gene expression as a response to chemotherapy, categorized based upon correlation to nodal status. Expect that no more than 10% of tumors will be unable to have tumor assessed on both pre- and post- chemotherapy tumor specimens.

2.5 Study Design:

Open-label, stratified, two arm design. All patients receive same initial standard preoperative chemotherapy and surgical resection. Patients will then be assigned to either standard postoperative chemotherapy if node negative at surgery or standard postoperative chemoradiation if node positive at surgery.

2.6 Number of Patients:

Forty patients.

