6.3.2.5 Adverse Event Assessment

6.4 Post-Treatment Surveillance (Follow-Up)

6.4.1 After completion of adjuvant chemotherapy, subjects will undergo follow-up, every 3 months, +/- 14 days, for a total of 36 months from the date of surgery.

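### Removal for non-compliance, and withdrawal not split into treatment and follow-up, end outcome collection, so recurrence data are lost avoidably and possibly informatively

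*Combined protocol and SAP*

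**What the plan says.** Section 8 contains three provisions that bear on this point.

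- **Who counts.** "All patients who are enrolled on the study and begin any of their intended post-operative adjuvant therapy will be counted as evaluable for the study".
- **Who is kept after stopping treatment.** The listed criteria are unacceptable toxicity, a toxicity delay over 2 weeks, and "Treatment delay for any other reason > 3 weeks". For all three, "Patients who discontinue treatment for these reasons will remain on protocol and will move on to surveillance/follow-up for disease recurrence".
- **Who leaves.** "The patient may withdraw from the study at any time for any reason". In addition, "an investigator may remove a patient from the study for non-compliance with study protocol at any time". Of both groups it says: "Patients removed from the study for these reasons will be replaced".

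Section 6.4.1 sets the follow-up schedule: "After completion of adjuvant chemotherapy, subjects will undergo follow-up, every 3 months, +/- 14 days, for a total of 36 months from the date of surgery". Footnote 7 to each schedule in Appendix I ends that follow-up if the patient comes off study. For patients going off study, Section 12 asks for one closing summary giving the reasons for stopping protocol treatment. It asks for no later outcome.

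The outcomes affected are secondary. Section 2.4 states: "The recurrence rate while on trial will be reported for the two arms of the trial, and compared to historical controls". Section 10 adds time to recurrence and recurrence-free survival, summarized by Kaplan-Meier methods. Neither section gives a censoring or missing-data rule.

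**The concern.** Section 8 has a route out of the study that does not depend on the patient's wishes. An investigator can end all data collection on someone who has not withdrawn consent, on the ground of non-compliance. It also offers only one kind of withdrawal, from the study as a whole. A patient who wants no more treatment but would accept follow-up can therefore be recorded as a full withdrawal.

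Both routes can be used during treatment, when the reason for leaving may be connected with how the patient is doing. If leavers have a different recurrence risk from those who stay, the recurrence rate and the Kaplan-Meier estimates for the arm no longer describe everyone assigned to it by nodal status, which is what the secondary objective in Section 2.2 asks for. The planned comparison with historical controls would carry the same distortion.

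**Working it through.** **1. Who is followed, reading Section 8 with Section 6.4**

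| Patient | Outcome follow-up under the text |
|---|---|
| Completes treatment | Yes, to 36 months from surgery (6.4.1) |
| Stops for toxicity, or for a toxicity delay over 2 weeks | Yes (Section 8) |
| Stops for any other reason, stays enrolled, passes 3 weeks | Yes (Section 8, third criterion) |
| Removed by the investigator for non-compliance | None provided; replaced |
| Withdraws from treatment only | No such category; treated as withdrawal from the study unless the 3-week criterion is applied first |
| Withdraws consent altogether | None; unavoidable |

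The avoidable loss is in the fourth and fifth rows. The removal power applies at any time, so two patients who miss the same treatment could be treated differently: one followed to 36 months, the other lost, at the investigator's discretion.

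**2. The plan's own precision figure**

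Section 10 gives Wilson 95% half-widths, at a 50% rate, of at most 17 points (n = 30) and 26.5 points (n = 10).

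Half-width = z/(1 + z²/n) × √(p(1−p)/n + z²/(4n²)), with p = 0.5 and z = 1.96.

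- n = 30: 16.8 points.
- n = 10: 26.3 points.

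Both reproduce. They give a yardstick for the bias below.

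**3. Possible bias in a simple recurrence proportion, Arm 2**

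From Section 10: n = 30 in Arm 2, and non-completion of up to 30% is tolerated, so k = 9. Section 3.2 says that under 50% completed in two earlier trials, so k = 15 is taken as a pessimistic case.

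Assumptions not in the documents: recurrence of 40% in completers; recurrence r of 40%, 60% or 70% in non-completers; half of the non-completers leave and drop out of the calculation; those who leave have the same risk as the other non-completers. Half of 9 or 15 is 4.5 or 7.5, read as expected counts.

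- Full-arm rate = [(30 − k) × 0.40 + k × r] / 30
- Observed rate = [(30 − k) × 0.40 + (k/2) × r] / (30 − k/2)

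| k | r | Full-arm rate | Observed rate | Understatement (points) |
|---|---|---|---|---|
| 9 | 40% | 12.0/30 = 40.0% | 10.2/25.5 = 40.0% | 0 |
| 9 | 60% | 13.8/30 = 46.0% | 11.1/25.5 = 43.5% | 2.5 |
| 9 | 70% | 14.7/30 = 49.0% | 11.55/25.5 = 45.3% | 3.7 |
| 15 | 40% | 12.0/30 = 40.0% | 9.0/22.5 = 40.0% | 0 |
| 15 | 60% | 15.0/30 = 50.0% | 10.5/22.5 = 46.7% | 3.3 |
| 15 | 70% | 16.5/30 = 55.0% | 11.25/22.5 = 50.0% | 5.0 |

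Equivalently, understatement = (number leaving / 30) × (r − observed rate). The sign depends on whether leavers recur more or less often than those observed. If they recur less often, the rate is overstated.

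**4. What can be said without assuming a risk for leavers**

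If m of n patients leave with unknown status, the arm's recurrence proportion is left open over a width of m/n: 3/30 = 10 points in Arm 2, and 1/10 = 10 points in Arm 1.

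**5. The denominator is not defined**

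Step 3 drops leavers. Section 2.4 counts recurrence while on trial, and Section 8 counts everyone who starts therapy as evaluable. The documents do not say whether leavers stay in the denominator. If they did, with a 40% risk in everyone and 4.5 leaving before recurrence, the reported rate would be 0.40 × 25.5/30 = 34%. This is a separate consequence of the missing rule and is not added to the range in step 3.

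**The case against.** The strongest reply is the third discontinuation criterion. It covers a delay of more than 3 weeks for any reason, so a patient who declines further cycles but stays enrolled meets it and is sent to surveillance. That stands. A reader might infer that Section 8 follows only toxicity cases, or that a patient who stops by choice must leave the study. The text does not support either reading.

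Section 6.4.1 speaks of completing chemotherapy, and a reader might infer that it shuts out early stoppers. It does not, because Section 8 expressly sends them to the same surveillance. The mismatch is editorial.

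The direction of bias is not established. Nothing in the documents describes the recurrence risk of patients who withdraw or are removed, and many who stop because they are unwell would be kept under the three criteria. A reader might infer that the estimates must look too favorable, but equal risk gives no bias in step 3.

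Larger figures are also tempting. If every non-completer left, the same assumptions would give an understatement of 6 to 15 points (46% to 55% in the full arm against 40% observed). That would require losing the very patients whom Section 8 retains, so it is not a fair reading of the plan. Kaplan-Meier estimation also keeps leavers' time at risk and any recurrence before exit, so deleting them outright, as step 3 does, is a rough approximation.

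Finally, up to about 5 points is small beside a half-width of about 17 points in Arm 2, and the outcomes are secondary. This limits severity. It does not justify an avoidable loss: a wide interval does not correct bias, and with 10 patients in Arm 1 each lost patient matters.

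**Conclusion.** The point holds in a limited form. Section 8 retains most early stoppers. It still lets the investigator end outcome collection for non-compliance without withdrawal of consent, does not distinguish stopping treatment from refusing follow-up, and replaces those who leave without collecting their later outcomes. The resulting loss of recurrence and survival data is avoidable and may be informative.

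Size and direction cannot be determined from the documents. Under the assumptions in the working (9 to 15 of 30 not completing, 40% recurrence in completers, 40 to 70% in non-completers, half of the non-completers leaving and dropped from the calculation), understatement in Arm 2 runs from 0 to about 5 points. Loss after full withdrawal of consent would remain under any wording.

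Severity is minor to moderate, because these are secondary outcomes of a feasibility pilot. The same section also replaces leavers while counting everyone who starts therapy as evaluable. That bears on the primary completion rate and needs its own resolution.

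**What to change.** - **Section 8.** State that removal for non-compliance, or a patient's choice to stop, ends protocol treatment only. Continue to collect recurrence and survival status under Section 6.4 to 36 months after surgery, on the same terms as for other patients, unless the patient withdraws consent to follow-up. Record which kind of withdrawal occurred.
- **Section 10.** State that all patients who started therapy stay in the recurrence analyses of their assigned arm, and that a patient who withdraws consent to follow-up is censored at the last disease assessment.
- **Section 6.4.1 and footnote 7 of Appendix I.** As an editorial matter, let follow-up start after completion or early discontinuation of treatment.

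The criteria for stopping treatment are unchanged.

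The cost is an amendment and a few more patients to follow, using visits and data items that Section 6.4 already contains. Some of these patients will miss visits and need a chart or telephone check. Section 8 defines recurrence by surveillance imaging, so a telephone call can give survival status, but recurrence will need imaging results from the clinical record.
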